- Adverse events will be collected from the time of study drug administration through the last day of the subject's participation in the study. Serious adverse event reporting will begin at the time informed consent is obtained and will end 30 days after the last dose of study drug. s)
  - BMI will be calculated based on height and body weight.
  - Weight to be obtained with a calibrated scale with appropriate range and resolution. Subject must remove shoes and bulky layers of clothes n t
    - Screening ECGs will be collected in triplicate (at least two (2) minutes apart). All other ECGs will be single ECGs.  $\widehat{}$
- where the form has been completed incorrectly. The completed S STS source document will be mailed back to the clinic or returned at the next study visit Visit Three (3) will be completed by telephone or videoconference. The subject will be asked to complete the printed copy of the S-STS given to them at their Baseline Visit while communicating with the site staff. The staff will review the subject's answers to the S-STS and recommend corrections, only to be filed in the subject's chart and entered into the eCRF system. (M
  - A safety follow-up call should be completed 7-10 days after Visit 6 completion. Final safety follow-up call to be made  $30 (\pm 5 \text{ days})$  days after Visit 6 completion. Investigator may ask subject to return for Unscheduled Visit, as needed. X)

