- 6. Known history of significant cardiovascular condition, such as myocardial infarction within the past year, or moderate to severe congestive heart failure (New York Heart Association (NYHA) Class III or IV); evidence of current uncontrolled cardiac arrhythmias, angina, or electrocardiographic evidence of acute ischemia or clinically significant conduction system anomalies; QTcF >450 msec (males) or >470 msec (females), or uncontrolled hypertension characterized by resting systolic blood pressure >160 mm Hg or resting diastolic >100 mm Hg, or clinically significant hypotension in the judgement of the Investigator as characterized by resting systolic blood pressure <90 mm Hg or resting diastolic blood pressure <60 mm Hg accompanied by symptoms such as lightheadedness, dizziness, and profound fatigue or signs such as irregular heartbeat.
- 7. Pulse rate <45 bpm or >90 bpm.
- 8. History of Huntington's disease, Parkinson's disease, Alzheimer's disease, multiple sclerosis, or a history of seizures (with the exception of childhood febrile seizures), epilepsy, or stroke.
- 9. Positive serology test result for HIV or current hepatitis B or C infection, or other ongoing infectious disease that the investigator considers clinically significant.
- 10. Concomitant use of protocol specified prohibited medications from which subject is unable to wash out (see Section 8.7 of the protocol for Concomitant Medications Restrictions).
  - a. Washout from excluded medication allowed only if the Investigator deems it medically appropriate.

- b. Washout period should be completed during screening, with last dose being at least two (2) weeks prior to randomization (See Section 15.1 of the protocol for Disallowed Analgesic and Other Medications).
- 11. Current or recent (within 12 months of screening) history of a substance use disorder including cannabinoid use disorder.
- 12.
  - a. Visit 1: Positive urine drug screen for benzodiazepines or opioids inconsistent with current prescriptions, psychoactive cannabinoids (e.g., marijuana, THC) inconsistent with subject reported use, PCP, cocaine, or amphetamines at Visit 1.
  - b. Visit 2: Positive urine drug screen for benzodiazepines inconsistent with protocol specified allowed prescriptions, psychoactive cannabinoids (e.g., marijuana, THC) inconsistent with subject reported use, PCP, opioids, cocaine, or amphetamines at Visit 2.

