#### 9.3.4. Electrocardiogram

Triplicate ECGs with a minimum of a two minute interval between each ECG will be collected at screening, and a standard 10-second ECG will be collected at baseline, week 8 and week 12/ET after at least five (5) minutes of supine rest and prior to blood sample collection, if possible. The device will be a Spaulding (Spaulding Medical, West Bend, WI) electrocardiogram (ECG) device that acquires a 12-lead ECG. The ECG data will be submitted to the designated ECG laboratory cardiologists for measurements and diagnoses.

The Principal Investigator or qualified Sub-investigator will review all ECG interpretations and interval duration measurements for clinical significance. Standard ECG parameters will be measured. Clinically significant, abnormal 12-lead ECGs should be repeated. Clinically significant ECG changes should be recorded as an adverse event.

The Spaulding ECG device should be used for all assessments during the study unless it is nonoperational, in which case another ECG may be performed locally and transmitted to Spaulding for central reading via printout.

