6.2.11 Electrocardiogram Data

For electrocardiogram (ECG) data recorded on continuous scales, if more than one value (for instance, triplicate recordings) is recorded at a time point (i.e., date), the mean value rounded to the integer will be presented. in the event that one reading is missing, the average of the available two readings will be used for the analysis. Furthermore, if only one reading is available, this reading will be used for the analysis.

For overall interpretation if more than one interpretation is recorded, the most severe (worst case) interpretation will be presented.

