6.12.3 Vital Signs

Descriptive statistics for observed values and changes from baseline in the following vital signs will be tabulated at each post-baseline visit:

Systolic blood pressure (mmHg)

- Diastolic blood pressure (mmHg)
- Pulse rate (bpm)
- Body weight (kg)

All vital signs measurements throughout the study will be listed.

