6.12.5 Electrocardiogram Data

Descriptive statistics for observed values and changes from baseline in the following ECG variables will be tabulated at each post-baseline visit:

- Heart rate (bpm)
- PR interval (ms)
- RR interval (ms)
- QRS complex (ms)
- QT interval (ms)
- QTc interval (ms) [Bazett's formula QTcB]
- QTc interval (ms) [Fridericia's formula QTcF]

Shift tables in relation to the overall interpretation (Normal, Abnormal Not Clinically Significant [NCS], and Abnormal Clinically Significant [CS]) from baseline to each post-baseline visit will be presented.

All ECG assessments throughout the study will be listed.

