16.2.8.5 Vital Signs Data - Safety Population IP 16.2.8.6 Electrocardiogram Data - Safety Population IP 16.2.8.7 Physical Examination Data - Safety Population IP 16.2.8.8 Neurological Examination Data - Safety Population IP 16.2.8.9 Urine Pregnancy Testing Data - Safety Population IP	16.2.8.3	Thyroid Panel Data - Safety Population	IP	
16.2.8.6 Electrocardiogram Data - Safety Population IP 16.2.8.7 Physical Examination Data - Safety Population IP 16.2.8.8 Neurological Examination Data - Safety Population IP 16.2.8.9 Urine Pregnancy Testing Data - Safety Population IP	16.2.8.4	Serology Data - Safety Population	IP	
16.2.8.7 Physical Examination Data - Safety Population IP 16.2.8.8 Neurological Examination Data - Safety Population IP 16.2.8.9 Urine Pregnancy Testing Data - Safety Population IP	16.2.8.5	Vital Signs Data - Safety Population	IP	
16.2.8.8 Neurological Examination Data - Safety Population IP 16.2.8.9 Urine Pregnancy Testing Data - Safety Population IP	16.2.8.6	Electrocardiogram Data - Safety Population	IP	
16.2.8.9 Urine Pregnancy Testing Data - Safety Population IP	16.2.8.7	Physical Examination Data - Safety Population	IP	
	16.2.8.8	Neurological Examination Data - Safety Population	IP	
16.2.8.10 Urine Drug Screening Data - Safety Population IP	16.2.8.9	Urine Pregnancy Testing Data - Safety Population	IP	
	16.2.8.10	Urine Drug Screening Data - Safety Population	IP

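### No by-arm counts of QTcF, blood-pressure or pulse exceedances are planned, and a same-day repeat ECG is averaged with the abnormal tracing that prompted it

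*SAP*

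**What the plan says.** For ECG intervals, including QTcF, SAP Section 6.12.5 states: "Descriptive statistics for observed values and changes from baseline in the following ECG variables will be tabulated at each post-baseline visit". Section 6.12.3 has the parallel sentence for blood pressure, pulse and weight: "Descriptive statistics for observed values and changes from baseline in the following vital signs will be tabulated at each post-baseline visit". Section 6.3.4 defines these statistics as n, mean, median, SD, minimum and maximum, and Section 6.3.6 presents them by treatment group. The outputs are Tables 14.3.6.1 (vital signs) and 14.3.6.2 (ECG). ECG also has Table 14.3.6.3, a shift in the overall reading (normal, abnormal not clinically significant, abnormal clinically significant). Vital signs have no categorical table. Individual readings go to subject listings: "16.2.8.5 Vital Signs Data - Safety Population IP 16.2.8.6 Electrocardiogram Data - Safety Population".

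When an ECG parameter on a continuous scale has more than one value "recorded at a time point (i.e., date), the mean value rounded to the integer will be presented" (SAP Section 6.2.11). For overall interpretations the same section keeps the worst case.

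Protocol Table 3 plans a triplicate at Screening and then says: "All other ECGs will be single ECGs". Post-baseline ECGs fall at Weeks 8 and 12. On repeats, Protocol Section 9.3.4 says: "Clinically significant, abnormal 12-lead ECGs should be repeated". It also has clinically significant changes recorded as adverse events, and Section 12.7.3 summarises clinically significant deteriorations as TEAEs.

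Protocol Section 7.2 gives numeric entry limits: QTcF above 450 ms (men) or 470 ms (women); systolic pressure above 160 or diastolic above 100 mm Hg; systolic below 90 or diastolic below 60 mm Hg with symptoms; pulse below 45 or above 90 bpm. Neither document uses a numeric limit for these measures after entry.

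**The concern.** Safety and tolerability form part of the primary objective. The protocol's introduction describes tolerability for up to 4 weeks of dosing, this study doses for 12, and SAP Section 8 plans no DSMB analysis. The final by-arm tables are therefore the main planned aggregate view of ECG and vital-sign safety.

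A drug effect on QTc, pulse or blood pressure may appear as large changes in a few subjects with little movement in the rest. Summary statistics by visit are poorly suited to that pattern, and a count of subjects beyond a limit is the direct display. The SAP gives laboratory values more: normal-range shift tables (Section 6.12.2) and numeric liver limits (Section 6.2.25).

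The averaging rule adds to the gap. It reads as written for the Screening triplicate but applies to any date. After Screening, apart from technical repeats, a second tracing on the same date is most likely to exist because the first was abnormal. The rule then falls selectively on abnormal values.

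**Working it through.** **1. Arm size.** SAP Section 4: difference 0.73, SD 1.7, two-sided 0.05, about 80% power, 15% drop-out. Per arm: 2 × (1.960 + 0.8416)² × 1.7² / 0.73² = 85.1, so 86. With drop-out: 86 / 0.85 = 101.2, so 102. Total 204, which matches the plan. It is used here only for the arm size.

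**2. Which planned output would show a by-arm count?**
- Tables 14.3.6.1 and 14.3.6.2: summary statistics, no count.
- Table 14.3.6.3: counts by overall reading. All ECG findings are mixed and there is no QTc limit, so a QTcF above 450 or 470 ms not read as clinically significant is not counted as such.
- TEAE tables: counts, but entry depends on investigator judgement with no numeric limit.
- Listings 16.2.8.5 and 16.2.8.6: individual values, no count.

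**3. Averaging (assumed readings).** (520 + 460) / 2 = 490 ms. (460 + 436) / 2 = 448 ms, which takes a man from above the 450 ms entry limit to below it. The maximum in Table 14.3.6.2 is built from these averaged values.

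**4. Sensitivity of the mean.** The documents give no SD for QTcF or systolic pressure, so the SDs, excursion sizes and numbers affected are assumptions. Standard error of the arm difference = SD × √(2/102).
- QTcF, four subjects rising 60 ms: shift 4 × 60 / 102 = 2.35 ms. Standard error 2.10 ms (SD 15) or 2.80 ms (SD 20). Ratio 1.12 or 0.84.
- The same with 87 per arm at Week 12 (102 × 0.85 = 86.7): shift 4 × 60 / 87 = 2.76 ms. Ratio 240 / (SD × √174) = 1.21 (SD 15) or 0.91 (SD 20).
- Systolic pressure, five subjects rising 40 mm Hg: shift 5 × 40 / 102 = 1.96 mm Hg. Ratio 0.93, 0.70 or 0.56 for SD 15, 20 or 25.

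Shifts of about one standard error or less do not stand out from chance. A count would show 4 against 0, or 5 against 0.

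**5. The maximum.** It describes one subject per arm and visit. Four subjects with a high peak in one arm and one in the other can give similar maxima.

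**6. Unscheduled readings.** Under SAP Sections 6.2.12 and 6.2.13, an unscheduled reading mapped to a visit that already has a scheduled one gives way to it, and the handling it follows is to list the displaced record only. An extreme unscheduled value can thus be absent even from the tabulated minimum and maximum.

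**The case against.** The plan is not blind to excursions. Each arm's minimum and maximum, observed and change, are tabulated at every visit. A tracing that prompted a protocol repeat was judged clinically significant; under the worst-case rule in SAP Section 6.2.11 it stays in that category of the by-arm shift table whatever the repeat shows. Such changes are also to be recorded as adverse events, so the 520/460 ms example could appear by arm in two tables, with only its number softened. The protocol sets no timing for repeats: one on another date is not averaged, and the scheduled value takes precedence. How often averaging would occur is unknown. A vital-sign change can also be an adverse event, because the general definition in Protocol Section 9.4.1 includes signs and physiological observations. The limits in Protocol Section 7.2 are entry criteria, not on-treatment alert limits. The SAP already gives more than the mean changes that the protocol plans for vital signs (Section 12.7.4), and SAP Section 6 allows further tables.

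All of this is correct, and it bounds the point. It does not supply a count. The maximum is one subject, the shift table has no QTc limit, and the adverse-event route rests on judgement. Tables added after unblinding under SAP Section 6 would be open to the charge that their limits were chosen with the results in view.

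**Conclusion.** The gap is real and moderate: no by-arm count of QTcF, blood-pressure or pulse exceedances is planned, and averaging lowers the tabulated ECG value whenever a same-day repeat reads lower than the tracing that triggered it. It weakens the safety summary without invalidating it. The size rests on assumptions: about 0.8 to 1.1 standard errors for four subjects at 60 ms, with an assumed SD of 20 to 15 ms, and 30 ms lost from the tabulated value in the 520/460 example.

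A reader might infer that excursions are visible only in subject listings, or that averaging hides the abnormal ECG. The documents do not support either. The quoted list shows only that listings exist; minimum and maximum are tabulated by arm, the worst interpretation is retained, and clinically significant ECG changes reach the TEAE tables. Nor do the documents suggest an existing signal: Protocol Section 4 reports no clinically meaningful ECG or vital-sign change after a single dose.

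**What to change.** - **SAP Section 6.2.11:** limit averaging to the planned Screening triplicate. For later dates with more than one ECG, tabulate the scheduled (first) tracing, consistent with the precedence in Section 6.2.13. State how this sits with Section 6.2.2, which takes the last value before dosing, repeats included, as baseline. Keep the worst-case rule for interpretations.
- **SAP Sections 6.12.3 and 6.12.5, and Section 11:** add one descriptive by-arm table each, counting subjects whose worst single post-baseline value, including repeats and unscheduled readings, lies beyond limits fixed before unblinding. The numeric entry limits in Protocol Section 7.2, low-blood-pressure limits included, could serve as descriptive cut-offs only, with no bearing on subject management.
- **QTcF change:** the documents give no cut-off. If one is added, the sponsor should choose and justify it.

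Cost: a few sentences and two tables from data already collected, with slightly noisier single-tracing values on the few repeat dates.
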